### 8.2.1. Inclusion criteria

The data will be collected for patients who have met all of the following inclusion criteria:

1. Diagnosis of non-valvular atrial fibrillation (NVAF);
2. New initiation of anticoagulation therapy (apixaban or warfarin) due to the ischemic event (stroke/TIA) meaning patients previously not anticoagulated due to diagnosis of NVAF;
3. Indication to anticoagulation therapy as a secondary stroke prevention within 7 to 30 days after the stroke/TIA event;
4. Apixaban arm: genetically determined higher sensitivity to warfarin;
5. Patients whose status allowed oral treatment with apixaban/warfarin;
6. Age  $\geq 18$ ;
7. Access to patient's records of the first 6 months of the warfarin/apixaban treatment.

### 8.2.2. Exclusion criteria

Patients meeting any of the following criteria will not be included in the study:

8. Diagnosis of valvular disease;
9. Treatment with other anticoagulants in previous 6 months due to other the NVAF indication;
10. Treatment or prophylaxis of deep vein thrombosis or pulmonary embolism;
11. Contraindications according SmPC of Eliquis.

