Nonetheless NOACs were categorized as a second line treatment due to the restriction of SUKL (local regulatory authority) in Czech Republic and therefore Czech patients are primarily treated with warfarin (including patient post stroke/TIA) and NOACs treatment can be initiated only in case of defined contraindication. Czech Cardiology Society, Society of Ambulatory Specialist together with main Czech Public Insurance House (VZP) defined number of conditions where safe and efficacious anticoagulation therapy by VKA cannot be adequately ensured. Prescription of NOACs as first line therapy is allowed in these defined situations . One of the situations is described as higher sensitivity to warfarin. There are two variants of two genes, CYP2C9 and VKORC1, account for 30-50% of the variability in dosing of warfarin. The prevalence of CYP2C9 (allele \*1, \*2 and \*3) and VKORC1 (-1639 G and A alleles), and their combinations in Czech population was analyzed and about 30% of the Czech healthy subjects have genetically determined higher sensitivity to warfarin. Individuals with higher sensitivity to warfarin are eligible for first line NOACs treatment in secondary prevention of stroke.

Additionally there is no healthcare resource use (hospitalization days, outpatient visits, and clinical events) comparison of apixaban to warfarin available in the Czech Republic. The most intensive resource use is expected in the first 6 months after stroke, especially because of a high risk of the event recurrence. Considering that there are less outpatient visits, less monitoring needed and lower risk of the complications and adverse events expected with apixaban. Real-world data about the impact of different treatment strategies on healthcare resource use and costs are essential arguments for establishing the clinical value of new therapies.

In the light of this situation we have designed this study to compare the healthcare resource use in patients who use warfarin or apixaban in secondary stroke prevention as a first line therapy.

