## 7. RESEARCH QUESTION AND OBJECTIVES

The primary objective of the study is:

- Description of direct costs related to warfarin/apixaban treatment during the first 6 months of the secondary stroke prevention in NVAF patients.

The secondary objectives of this study are:

- Comparison of direct costs related to warfarin/apixaban treatment during the first 6 months of the secondary stroke prevention in NVAF patients;
- Number of hospitalization days in the first 6 months of the treatment;
- Number of ischemic/hemorrhagic strokes in the first 6 months of the treatment;
- Number of ischemic events in the first 6 months of the treatment;
- Number of major/minor hemorrhagic events in the first 6 months of the treatment;
- Mortality rates in both cohorts;
- Number and costs of medical procedures directly related to the treatment in the first 6 months (visits, hospitalizations, labs, diagnostics, etc.);
- Overall safety (adverse events) of the treatment.

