## 8.9. Strengths and limitations of the research methods

The study design is considered to be the main strength of this study. It brings a unique opportunity to compare the outcomes of two cohorts of patients fulfilling the same inclusion criteria. Another strength of the design is data collection in real-world setting without any patient's selection according subgroups characteristics. The main limitation of the research may be a random distribution of patients on warfarin/apixaban treatment.

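### Criterion 11 screens for contraindications to apixaban only and criterion 5 is ambiguous, so the secondary between-arm comparisons may include apixaban patients with few or no warfarin counterparts

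*Combined protocol and SAP*

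**What the plan says.** **Eligibility.** Among the exclusions in 8.2.2, which apply to both arms, criterion 11 removes patients with "Contraindications according SmPC of Eliquis". Criteria 8 to 11 contain no equivalent for warfarin. Two inclusion criteria in 8.2.1 also bear on the point. Criterion 4 reads "Apixaban arm: genetically determined higher sensitivity to warfarin" and sets no genotype condition for the warfarin arm. Criterion 5, for both arms, reads "Patients whose status allowed oral treatment with apixaban/warfarin".

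**Access to NOACs.** Section 6 states that in the Czech Republic "NOACs treatment can be initiated only in case of defined contraindication". It refers to a list of conditions agreed by professional societies and the main insurer, under which first-line NOAC prescription is permitted, and adds: "One of the situations is described as higher sensitivity to warfarin". The protocol does not reproduce the list; it cites it as reference 29.

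**Use of the data.** The primary objective in section 7 is descriptive. The first secondary objective is "Comparison of direct costs related to warfarin/apixaban treatment during the first 6 months". Section 8.7 compares endpoints by differences in means, medians or proportions at the 0.05 level and describes no adjustment. Section 8.9 counts it as a strength that the study can "compare the outcomes of two cohorts of patients fulfilling the same inclusion criteria". Table 1 in 8.3 has no variable for why a NOAC was chosen or warfarin avoided.

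**The concern.** A comparison of two drugs is easiest to interpret when every patient in it could have received either. Criterion 11 moves the warfarin arm towards that condition by removing patients who could not have had apixaban. Nothing clearly does the same for the apixaban arm.

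Criterion 4 requires the genotype but does not require it to be the only reason for choosing apixaban. A patient with the genotype and a second listed condition is eligible for the apixaban arm, and such patients may be rare or missing among those started on warfarin. If the second reason is related to bleeding risk, adherence or resource use, part of any cost or event difference would reflect who was selected, not the drug. With no field in Table 1 for such a reason, the analysis could neither detect these patients nor set them aside.

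**Working it through.** There is no plan figure to reproduce: 8.5 says the sample size was not statistically determined, and no effect size, SD or power is given. The check is therefore textual, followed by an illustration of scale.

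**1. What criterion 5 requires.** Two readings are possible.

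- *Only the drug received.* Criterion 7, "Access to patient's records of the first 6 months of the warfarin/apixaban treatment", uses the slash this way. Under the alternative reading, criterion 11 would be largely redundant, and criterion 5 would sit awkwardly with criterion 4, which requires a feature that section 6 treats as a reason against VKA therapy.
- *Both drugs.* Criterion 2 and section 8.2 join the drug names with the word or when they mean the drug of the arm, so a slash could mean something else. Criterion 5 would also add little if it meant only the drug received, because criterion 2 already requires that drug to have been started.

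The text does not settle it, and whoever abstracts the charts has to apply one reading.

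**2. Who could be affected.** Criterion 4 keeps out patients given apixaban solely for another reason. What remains is patients with the genotype and a second reason against warfarin. Section 6 makes such patients possible but gives no count.

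**3. Scale, by assumption.** Let q be the share of the apixaban arm with a second reason, r the corresponding share of the warfarin arm, and d the difference in mean cost, in SD units, between such patients and the rest. With no drug effect:

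- bias = (q − r) × d
- SE of the difference in means with 120 per arm = √(2/120) = 0.129 SD; 95% half-width = 1.96 × 0.129 = 0.253 SD
- two-sided false-positive rate = Φ(−1.96 + bias/SE) + Φ(−1.96 − bias/SE)

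The 120 per arm is from 8.2 and the 0.05 level from 8.7. Two-sided testing, a normal approximation for independent arms, equal SDs, and q, r and d are my assumptions. Setting r = 0 (no counterparts at all) gives the largest bias for a given q and d:

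| q | patients of 120 | d | bias (SD) | false-positive rate |
|---|---|---|---|---|
| 5% | 6 | 0.5 | 0.025 | 5.4% |
| 10% | 12 | 0.5 | 0.05 | 6.7% |
| 20% | 24 | 0.5 | 0.10 | 12.1% |
| 30% | 36 | 1.0 | 0.30 | 64% |

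In cost terms, the shift in the apixaban mean relative to its remaining patients is share × (cost ratio − 1). A 10% share at a ratio of 1.25 gives 0.10 × 0.25 = 2.5%; a 30% share at a ratio of 2 gives 0.30 × 1.0 = 30%. If these patients cost less than the rest, the sign reverses.

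**4. Which objectives are touched.** A description of costs within each arm involves no contrast and is not biased by this. The secondary comparisons of cost and events are contrasts, and 8.7 leaves them unadjusted.

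**The case against.** The strongest reply is that the gap may not exist. On the both-drugs reading, criterion 5 already removes patients unsuitable for warfarin, and criterion 4 has narrowed the group to those with two reasons. No passage shows that any such patient exists. This stands as a limit on certainty. It does not remove the need to state which reading applies.

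A reader might infer that patients with a second reason are necessarily absent from the warfarin arm. The documents do not support that. Section 6 says NOAC prescription is permitted in the listed situations, not required, and that Czech patients are mainly treated with warfarin. A condition that makes VKA therapy hard to deliver adequately is also not the same as being unable to receive warfarin. Any warfarin patients of this kind make r positive and shrink the bias.

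A reader might also infer that no analysis could repair the imbalance, or that every condition on the insurer and society list should be an exclusion. Neither follows. Once the reason is recorded, the comparison can be restricted to patients without one. The list itself is not in the documents, so the effect of excluding all of it cannot be judged.

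Finally, the study is exploratory and its primary objective descriptive, and narrowing eligibility costs some real-world representativeness. That argues for a light fix, not for leaving the wording as it is, since between-arm comparison at the 0.05 level is planned.

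**Conclusion.** The point holds in a limited form. The contraindication rule names one drug only, and criterion 5 does not clearly supply the other half. With genetic sensitivity only one of several routes to a NOAC, some apixaban patients may have had a further reason against warfarin and few or no counterparts in the other arm.

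The size is unknown. Under the assumptions shown, the effect runs from negligible (5.4% false positives at a 5% share and 0.5 SD) to serious (64% at a 30% share and 1.0 SD). The documents do not say where in that range the study lies, or in which direction, so these figures illustrate scale and are not evidence of material bias.

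Only the secondary comparisons are exposed. The matter is separate from, and less certain than, the non-comparability caused by requiring the genotype in one arm only. That requirement by itself contradicts the statement in 8.9 that both cohorts meet the same criteria, and it would remain after the fix below. I class this as a cheap improvement.

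**What to change.** Before data collection starts:

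1. **Make the rule symmetric.** State in criterion 5 or criterion 11 that patients in both arms had no documented contraindication under the SmPC of either drug at the index date, genetically determined higher sensitivity to warfarin aside. This also settles the meaning of criterion 5.
2. **Record the reason.** Add one e-CRF field, in both arms, for any other documented reason against warfarin at the index date, and list it in Table 1.
3. **Add a sensitivity analysis.** Repeat the between-arm comparisons in patients with no such other reason. Use this instead of excluding every condition on the insurer and society list.

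**Cost.** One more abstracted item per chart and a somewhat smaller comparison set. If 20% of the apixaban arm were set aside, 96 would remain against 120, and the 95% half-width would go from 0.253 to 1.96 × √(1/96 + 1/120) = 0.268 SD.

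Step 1 may also reduce the number of eligible apixaban charts. As an assumption, if it removed 10% to 30% of them, reaching 120 would take about 120/0.90 = 133 to 120/0.70 = 171 otherwise eligible charts. The extension to 6 months in 8.2 may not make this up, because it lengthens abstraction without enlarging a single centre's pool of charts. If charts run short, steps 2 and 3 can still be done without step 1, provided criterion 5 is clarified.

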### 8.3. Variables

**Table 1:** Table of variables

Variable	Role	Data source(s)	Operational definition
Age, Sex, BMI, date of index event (stroke/TIA diagnosis), date of indication to warfarin/apixaban treatment (index date)	Demographic data	Medical records	Specified in e-CRF
CHA2-DS2-Vasc score, HAS-BLED score	Outcome	Medical records	Specified in e-CRF
Therapy after index event, prior to warfarin/apixaban treatment	Exposure	Medical records	Specified in e-CRF
Warfarin/apixaban therapy information (dosage; number of INR measurements in warfarin arm)	Exposure	Medical records	Specified in e-CRF
Number and type of resource use during the first 6 months of warfarin/apixaban treatment (outpatient visits, diagnostic procedures, labs, medication, hospital admissions)	Outcome	Medical records	Specified in e-CRF
Amount, type, severity and cost of ischemic events	Outcome	Medical records	Specified in e-CRF

Amount, type, severity and cost of major/minor hemorrhagic events	Outcome	Medical records	Specified in e-CRF
Adverse events	Outcome	Medical records	Specified in e-CRF

*Index date = The index date will be the first date of OAC prescription indicated for secondary stroke/TIA prevention.*

*Index event = The index event will be the first stroke/TIA event based on which the OAC treatment will be initiated.*

*Index event date = The index event date will be the date of first stroke/TIA event based on which the OAC treatment will be initiated*

*Therapy after index event, prior to warfarin/apixaban treatment (Aspirin, clopidigrel, Trombolytics (rhu-tPA - alteplase, urokinase), Anticoagulants (heparin, heparinoids), other)*

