### **8.7. Data analysis**

The statistical analyses will be descriptive and exploratory. Given the nature of the study, which is exploratory, it is not designed to confirm or reject predetermined hypotheses.

Categorical outcomes will be summarized by the number and percentage in each category. Continuous outcomes will be summarized by mean, standard deviation, median, minimum and maximum values.

All analyses will be based on the full analysis set, comprising all subjects enrolled into the study.

The paired tests will be applied in the detailed analyses. Relevant endpoints will be compared using the differences in mean / median or proportion. Statistical significance will be assessed at a significance level of 0.05. All statistical analyses will be conducted using STATA version 13.1.

**Table 2:** Table of descriptive analyses

Variable	Categorical outcome	Continuous outcome
Age		X
Sex	X	
Body height, weight, BMI		X
Period between stroke/TIA and start of secondary stroke prevention (duration in days)		X
Period between stroke/TIA and start of secondary stroke prevention (medication)	X	
CHA2-DS2-VASc Score		X
Stratification: (0, 1, 2-9)	X	
HAS-BLED Score		X
Stratification: (0-2, 3-9)	X	
Warfarin/apixaban dosage		X
INR measurements	X	
Number and type of outpatient visits, diagnostic procedures, labs, hospital admissions	X	
Cost of outpatient visits, diagnostic procedures, labs, medication, hospital admissions		X
Amount, type and severity of ischemic events	X	
Cost of ischemic events		X
Amount, type, severity of major/minor hemorrhagic events	X	

Cost of major/minor hemorrhagic events		X
Adverse events	X	

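### No listed baseline variable records whether the index event was a stroke or a TIA, or how severe it was, so the secondary cost comparison cannot be checked or adjusted for it from the listed variables

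*Combined protocol and SAP*

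**What the plan says.** The demographic row of Table 1 (section 8.3) begins "Age, Sex, BMI, date of index event (stroke/TIA diagnosis" and ends with the index date, with its operational definition left to the e-CRF. The words in brackets after the index event say what is being dated. No row separates stroke from TIA. The note under the table pools them: "The index event will be the first stroke/TIA event based on which the OAC treatment will be initiated".

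Type and severity do appear in Table 1, as "Amount, type, severity and cost of ischemic events" and in a matching row for hemorrhagic events, but both rows have the role of outcome. Table 2 (section 8.7) adds height, weight, the interval in days from the event to the start of prevention, the medication in that interval, and the two risk scores. It has no index-event type or severity either.

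Comparing direct costs between the arms is a secondary objective (section 7); the primary objective is to describe them. For comparisons section 8.7 says: "Relevant endpoints will be compared using the differences in mean / median or proportion", with significance judged at 0.05. It also announces paired tests without saying what the pairs are. It describes no covariate adjustment, matching or weighting.

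**The concern.** The cohort can run from a transient event to a stroke with lasting disability. Table 1 counts outpatient visits, diagnostics, laboratory tests, medication and admissions over the 6 months from treatment start, and section 6 expects resource use to be heaviest in the first 6 months after stroke. Continuing care for the index stroke can therefore fall inside the cost window, which makes severity a plausible driver of cost whichever drug was given.

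Treatment was not randomised. Criterion 4 in section 8.2.1 requires genetic sensitivity to warfarin in the apixaban arm only, and section 6 says NOACs were open only to patients in defined situations. The documents do not say which patients were genotyped or on what grounds. If the arms differ systematically in the share of severe index events, the crude cost difference carries that difference and would be read as an effect of the drug. With the listed variables nobody could see whether this had happened.

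**Working it through.** The plan gives no power, effect size, standard deviation or cost figure, so there is nothing of its own to reproduce. Section 8.5 says the size was not statistically determined; 120 + 120 = 240 agrees with section 8.2.

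**1. Do the outcome rows cover the index event?** Section 7 sets the window: "Number of ischemic events in the first 6 months of the treatment". Section 8.2.1 puts the index event before it: "Indication to anticoagulation therapy as a secondary stroke prevention within 7 to 30 days after the stroke/TIA event". Read together, the type and severity rows describe later events.

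**2. Can a listed variable stand in?** The prior stroke/TIA item of CHA2DS2-VASc is met by every patient here, so it cannot separate them by index-event type or severity; the rest of the score reflects other risk factors. Interim therapy (including thrombolytics) and days to treatment carry some information, but indirectly.

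**3. Possible size.** All inputs in this step are assumptions. Let a mild stroke or TIA cost 1, a severe stroke cost r, and the severe share be 0.30 in one arm and 0.30 + d in the other. With no drug effect:

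mean cost ratio = [1 + (r − 1)(0.30 + d)] / [1 + (r − 1)(0.30)]

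| d | r = 2 | r = 4 |
|---|---|---|
| 0.05 | 1.35/1.30 = 1.04 | 2.05/1.90 = 1.08 |
| 0.10 | 1.40/1.30 = 1.08 | 2.20/1.90 = 1.16 |
| 0.15 | 1.45/1.30 = 1.12 | 2.35/1.90 = 1.24 |

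**4. Effect on the test at 0.05.** This takes a two-sided test of independent groups, 120 per arm, normal approximation. The difference detectable with 80% power is (1.96 + 0.84) × √(2/120) = 0.36 SD. Suppose about 70% of index events are strokes, strokes cost g SD more than TIAs, and the stroke share differs by Δ. Then:

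- bias b = g × Δ
- SE = √(v × 2/120), where v = 1 + g² × the average of p(1 − p) over the arms
- false-positive rate = 1 − Φ(1.96 − b/SE) + Φ(−1.96 − b/SE)

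For g = 0.5 and Δ = 0.10: b = 0.05, v = 1 + 0.25 × 0.2075 = 1.052, SE = 0.132, b/SE = 0.38, rate 6.7%.

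| g (SD) | Δ = 0.10 | Δ = 0.30 |
|---|---|---|
| 0.25 | 5.4% | 8.9% |
| 0.5 | 6.7% | 20.6% |
| 1.0 | 10.9% | 56.9% |

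The bias runs from 0.25 × 0.10 = 0.025 SD to 1.0 × 0.30 = 0.30 SD, that is, from negligible to nearly the detectable difference.

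**5. How large is an ordinary chance imbalance?** For 30% against 40% severe with 120 per arm, SE = √(0.30 × 0.70/120 + 0.40 × 0.60/120) = √0.00375 = 0.061. A gap of 5 points is 0.8 SE, 10 points 1.6 SE and 15 points about 2.4 SE.

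**The case against.** The strongest case against has four parts.

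- **Nothing shows that the arms differ.** Entry to the apixaban arm rests on a genotype, and the documents do not link that genotype to stroke severity. Step 5 shows that 5 to 10 points can arise by chance, which the test's standard error already allows for. This stands: only a systematic imbalance biases the comparison, and none is demonstrated.
- **The costs may be only loosely tied to the index stroke.** The objectives concern costs related to the anticoagulant, the window opens at its first prescription, at least the first week after the event normally lies outside it, and patients had to be fit for oral treatment. All this could bring the cost ratio well below the assumed 2 to 4. It stands as a limit on size, but the resource-use row of Table 1 is not confined to drug-caused use.
- **The e-CRF may hold more.** It is not among the documents, and the Table 1 row on ischemic events states no time window. A reader might infer that severity is certainly collected only after treatment start, or that adjustment is impossible. The documents support less: no such baseline variable is listed, and the outcome role and the objectives point to later events.
- **The study is exploratory and its primary objective descriptive.** That limits the point to the secondary comparison, and to what readers make of two cost summaries side by side. Since section 8.7 adjusts for nothing, new fields alone would change no planned estimate.

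A reader might also take section 8.9 as conceding confounding. It says "The main limitation of the research may be a random distribution of patients on warfarin/apixaban treatment". The sentence is puzzling, but it speaks of a random distribution and cannot be cited as that admission.

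**Conclusion.** The point holds for the secondary cost comparison. Index-event type and index-stroke severity are absent from both variable tables, allocation is not randomised, and the planned differences are unadjusted, so imbalance on this plausible confounder can be neither shown nor removed using the listed variables.

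That severity is a main driver of 6-month cost is a reasonable inference, not something the documents state; section 6 points to the risk of recurrence. It would go too far to conclude that the comparison is biased, or in which direction. The range of about 4% to 24% depends wholly on the assumed cost ratio, base share and imbalance, and the true figure could be close to zero. What can be said is that the study as planned could not tell these cases apart.

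**What to change.** Before chart abstraction starts, add two baseline items to Tables 1 and 2 and the e-CRF:

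1. index-event type (ischemic stroke or TIA);
2. the severity or disability score charted at the index admission, with a code for not recorded.

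Report both by arm. In section 8.7, pre-specify an adjusted between-arm cost comparison for independent groups beside the crude one, for example a gamma model with log link containing index-event type, severity, age, sex, CHA2DS2-VASc and HAS-BLED. State how missing severity is handled, and either define the pairing behind the paired tests or remove them.

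The cost is two more abstraction fields at one center where a physician already transcribes each chart; no patient procedure is added. The documents do not say that a severity score is routinely charted, so some will be missing. Eligibility requires a stroke or TIA without asking which, but the diagnosis that confirms eligibility should usually supply the type. The e-CRF is described as anonymous, so adding the fields now is easier than returning to the charts later. The descriptive primary objective needs no change.
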